Study protocol and Statistical Analysis Plan for

A behavioral activation intervention administered in a 16-week freshman orientation course

Clinical Trials Registration Number: NCT04038190

Document date: 1/13/2020

Note: all information presented herein was reported in the following publication:

[name], [name], & [name] (2020) A behavioral activation intervention administered in a 16-week freshman orientation course: Study protocol. *Contemporary Clinical Trials*; 90: 105950. DOI: 10.1016/j.cct.2020.105950

Study Protocol

The present study will be a cluster-randomized trial testing the efficacy of BA administered in a semester-long (16 week) freshmen orientation course, compared to a standard orientation course (SO) for addressing alcohol use and related clinical outcomes. Thirty-six 36 course sections (18 course sections for BA and 18 for SO) will be conducted in total, with N=540 participants. Mediation analyses will test mechanisms of action and moderation analyses will test the efficacy of the intervention based on key variables of interest.

Randomization

Randomization will occur at the course level. Randomization will employ blocking across morning and afternoon times and will occur within years.

Participant Recruitment and Enrollment

In collaboration with the University Director of Orientations, 36 sections of the existing, semester-long UNIV 101 freshman orientation curriculum will be modified and taught by research study staff. Each section will be randomly assigned to a condition, with 18 sections assigned to BA and 18 assigned to SO. Students will enroll into the offered UNIV 101 course sections *independent of* the research study by registering with the University's standard online course registration system. The 36 sections will be paired such that BA and SO classes will be offered at the same time of day and will be matched for treatment contact time.

Students enrolled into the BA and SO course sections will be offered the opportunity to participate in the research assessment portion of the study during the first week of class. Students aged 18+ will provide written informed consent, and students under age 18 will be required to sign an assent form and to obtain written parental permission to participate.

Assessment Schedule

Participants will be assessed at three times during treatment (weeks 1, 7, and 15), all of which will occur during the first semester. At the end of the academic year (April of spring semester), students will complete a final 5-month follow up assessment to test durability of treatment effects. The study will also test longer-term (17-month) efficacy in a random subsample of 20% of participants in Years 2-4, which will occur at the end of participant's sophomore year. While an extended follow up assessment of all N=540 participants is beyond the scope of the project, the longer follow-up on a random subsample of participants will provide an initial indication of longer-term efficacy. The 17-month follow up will yield approximately n=100 participants (n=50 BA condition and n=50 standard orientation condition).

Assessments during the intervention (weeks 1, 7, and 15) will be conducted in the classrooms in which the courses will be run, to facilitate participation. At follow up(s), participants will be contact via text and email and scheduled to attend the follow up assessment(s) at a study lab, which is located centrally on campus. Participants will be provided an escalating incentive schedule to maximize attendance at follow up(s), as described below.

Incentives

Participants will receive extra credit in their UNIV 101 course for participating in Assessments 1-3, and will be compensated \$50 for completing Assessment 4, which will occur after the courses have finished. To ensure participation in the research will not be coerced, students will be offered alternative extra credit assignments that will require approximately the same amount of time as participating in the study. The subsample of students participating in Assessment 5 (17-month follow up) will receive \$75 for completing the final assessment.

Research Staff

Research assistants who will collect study data will not be affiliated with the courses and will be blinded to study condition. Likewise, clinical staff who lead the course sections will not be

involved in research assessment administration and will be blind to participant responses.

Course and Intervention Content

SO course. The standard orientation course, UNIV 101, is designed to facilitate student adjustment to academics and campus life. UNIV 101 courses meet twice weekly for 50 minutes each. The course content is structured around four main themes: 1) academic and personal wellness; 2) experiential learning; 3) social justice; and 4) skill building. Within these themes, lessons address a variety of subjects, from introductions to academic resources on campus (e.g., the university writing center, library, advising), tours of campus venues, presentations from speakers, and academic success topics such as time management. Students are required to develop an individualized academic plan during the course. Work to be completed outside of class is required and includes development of the academic plan, writing and reflection assignments, projects that facilitate goal setting, and academic projects such as an annotated bibliography assignment to facilitate academic information literacy.

BA course. The BA course will include all major instructional content of the standard orientation course (main themes and assignments), as well as the BA content. The BA content will replace the supplemental topics and sessions from the standard orientation course, thus retaining key SO content while incorporating BA content. The goal of BA for addressing alcohol use is to identify, develop and reinforce healthy behaviors that can serve as alternatives to alcohol use. In addition, BA supports students in identifying areas of importance and concern (e.g., stress after arriving on campus), and guides them to engage in reinforcing behavior that best addresses their concerns and aligns with their goals (e.g., engaging in self-care for stress management, in service of a goal to performing well in classes). The basic components of BA that will be used to achieve these outcomes are 1) facilitating students' engagement in self-

monitoring of daily activities; 2) guiding students to identify values within a variety of life areas; 3) identifying and engaging in reinforcing activities that align with their values; 4) providing support to engage in activities as identified. BA course sessions and content are summarized in Table 1.

Table 1. Behavioral Activation in UNIV 101: Course Content Overview		
Week	BA Content	BA Work Outside of Class
Week 1	Introduction of treatment rationale: focus on engaging in reinforcing activities to promote a rewarding college lifestyle; Introduction to daily monitoring	Daily monitoring of activities, ratings of activity enjoyment
Week 2	Life areas and values: students will be guided in identifying their values within various life domains	Daily monitoring of activities, ratings of activity enjoyment and importance
Week 3	Identification of activities that align with values; Planning activities using the daily monitoring form	Daily monitoring, ratings of activity enjoyment and importance, planning activities using the daily monitoring form
Week 4	Engaging support to complete planned activities	Daily monitoring, ratings of activity enjoyment and importance, planning activities using the daily monitoring form
Weeks 5-14	Periodic BA review sessions	Daily monitoring, ratings of activity enjoyment and importance, planning activities using the daily monitoring form
Note. BA= behavioral activation		

Materials for BA course. College students are technologically-savvy and mobile phone use in this population is extensive; 95% of college students own smartphones¹⁵. Thus, to facilitate use and engagement with BA materials (e.g., daily monitoring), all materials will be provided through a web-based platform that students will be able to access via any computer-based device (smartphones, computers, tablet devices). However, alternatives to the web-based platform will be offered to students who prefer to complete forms using paper.

Instructor training and supervision. The instructors will undergo extensive training before delivering treatment and will be supervised by the study's Clinical Supervisor. In addition,

weekly supervision will be provided. Manuals will be used at all times to ensure standardization of treatment. All course sessions will be audiotaped and participant confidentiality will be protected by storing all recorded data on a HIPAA-secured server.

Measures

Assessment will focus on three domains: (1) alcohol use and alcohol-related problems, (2) reinforcement processes (3) clinical health outcomes and moderators. Measures of treatment compliance and fidelity are also described below.

Alcohol Use and Problems

Alcohol use and problems in the past month will be assessed using two measures:

The *Alcohol Use Disorder Identification Test (AUDIT)*¹⁶ is a 10-item questionnaire designed to assess hazardous drinking and related problems. The AUDIT provides a total score, with 8+ indicating hazardous use^{17,18}. The AUDIT has also been examined as two subscales: alcohol consumption (items 1-3 focused on frequency and quantity) and alcohol problems (items 4-10 that assess consequences)¹⁹⁻²¹. The percent of participants above the clinical cutoff for the total score will be used in analyses, as well as both subscale scores. While the AUDIT was originally designed to assess a time interval of the past 12 months, researchers have assessed change in alcohol use and related problems in shorter time intervals of 1, 3, and 6 months^{14,22}. The present study will use the past month as the reference point for the AUDIT.

The *computerized Time Line Follow Back (TLFB-C)* will be used to assess daily alcohol use in standard drinks during the past month²³⁻²⁵. The TLFB-C has good test-retest reliability and evidence of convergent validity with the TLFB administered in-person among college

student samples^{26,27}. Heavy drinking occasions will be defined as 4+ drinks for females, or 5+ for males in one episode, in excess of the low risk drinking guidelines from the National Institute on Alcohol Use and Alcoholism²⁸. High-intensity drinking occasions will be defined as double the heavy drinking occasion criteria, or 8+ for females and 10+ for males.

Reinforcement Processes

Environmental reinforcement. The Adolescent Reinforcement Survey Schedule - Alcohol Use Version (ARSS-AUV) assesses the frequency of past-month engagement in and enjoyment derived from 45 activities²⁹. Each question is posed twice - once to assess the frequency and enjoyment of the activity while using alcohol and the once to assess the frequency and enjoyment of the activity while not using alcohol. Frequency and enjoyment items are summed to form respective scores and then multiplied to form subscales for alcohol-related reinforcement and alcohol-free reinforcement. The two subscales are used to calculate the outcome, the total reinforcement ratio (TRR) between alcohol-related and alcohol-free reinforcement.

Delay discounting. A computerized binary choice procedure will assess DD. On each DD trial, two hypothetical money rewards will be presented on the screen. One outcome will be an amount of money available immediately; the other outcome will be a larger amount of money (\$25, \$100) available after a specified delay (1 day, 1 week, 1 month, 6 months, 1 year, 5 years). Participants will indicate the preferred alternative with a click and the computerized algorithm will adjust the immediate reward over 6 trials to determine an indifference point for each amount/delay pairing. Indifference points will be used to calculate a delay discount rate. Subjects will be told to indicate preference on the task as if the outcomes were for real money; research has indicated the statistical equivalence of DD tasks for hypothetical and real rewards³⁰.

Clinical Outcomes and Moderators

Stress and depression. The Depression Anxiety Stress Scale-21 (DASS-21)³¹ is a 21-item measure that has subscales for stress, depression, and anxiety. The DASS-21 measures stress, anxiety, and depression on a dimensional scale and is appropriate for use in a non-clinical, college sample. Studies reported strong internal consistency reliability in clinical and nonclinical samples^{31,32}, including college students³³.

Binge eating. The Eating Pathology Symptoms Inventory (EPSI)³⁴ will be used to assess binge eating. The EPSI conceptualizes eating behavior on a dimensional scale and is appropriate for use in samples with and without eating disorders. The binge eating subscale will be used in the study, which includes items on overeating and loss of control eating. The EPSI has evidence for excellent discriminant and convergent validity in female and male college students^{34,35}.

Coping-motivated drinking. The Drinking Motives Questionnaire-Revised (DMQ-R), a measure designed to measure motives for drinking alcohol, will be used to assess coping-motivated drinking^{36,37}. In a variety of young adult and college samples, the DMQ-R has demonstrated high subscale internal consistencies and four factor structure stability^{38–40}. The coping scale has been reliably associated with alcohol problems among young adult and college samples³⁸.

Treatment Compliance and Fidelity

Treatment compliance. Adherence to treatment will be measured by determining participants' completion of daily monitoring forms, and with course attendance (where students will receive the intervention content).

Treatment fidelity. Audio recordings of treatment will be rated by independent raters (e.g., raters not otherwise associated with the treatment delivery) to assess instructor adherence to and competence with the treatment protocol, using separate rating checklists and scales developed for the SO and BA protocols. Two senior research assistants will be trained in BA components to perform therapist adherence checks. They will review 20% of all audiotapes and perform competency checks, ratings-based adherence checks, and address any issues with instructors. Their feedback will be implemented in later sessions. Instructors will be required to complete a fidelity checklist for every class session they conduct.

Statistical Power

Power analysis. A target course section N of 36 (N=18 BA and N=18 SO), with N=432 participants total, will be required to detect medium effect sizes ($d=.43$) for main outcomes. Each class is expected to contain 18-20 students and power analyses were conducted assuming an 85% consent rate and a 20% attrition at follow up. An 85% consent rate will yield 15 participants per class, or N=540 total. With a 20% attrition rate, we will achieve the N=432 participants (12 per course section cluster) necessary to detect our outcomes of interest. For mediation analyses, will have sufficient power to detect a correlation between a drinking outcome and BA at a given time point $>.20$.

Data Analysis Plan

We will use SAS PROC Mixed with full information Maximum Likelihood estimation to evaluate outcomes using general linear mixed models for continuous outcomes and SAS PROC GLIMMIX for binary outcomes. Assignment to treatment condition will occur at the class section level (level 3). Student observations (level 1), will be nested in students (level 2), which will be nested within class sections. Fixed effects for intervention condition (BA or SO), instructor, and

cohort will be included at the class section level. Sex will also be added as a fixed effect at level 2. This approach will result in models with appropriate standard errors for the clustered sample.

For aim 1 we will compare differences between BA vs control in likelihood of exceeding the clinical cut-off for risky drinking as a binary outcome, and alcohol consumption (AUDIT consumption questions) and alcohol-related problems (AUDIT problem questions) as continuous outcomes. In addition, we will test differences across conditions in high-intensity drinking. Separate models will be developed for each outcome. Of primary interest are the main effects of treatment condition on both the intercepts and slopes for each of the outcomes. For aim 3 exploratory analyses on stress, depression, and binge eating, outcomes will be modeled separately for each outcome using general linear mixed models.

Analyses will be conducted to determine whether changes in environmental reinforcement and delay discounting mediate the association between intervention condition and alcohol outcomes. Moderation analyses will be conducted to determine whether intervention efficacy depends on coping-motivated drinking at baseline, sex, or race/ethnicity.

References

1. Brown, S. A. *et al.* A Developmental Perspective on Alcohol and Youths 16 to 20 Years of Age. *Pediatrics* **121**, S290–S310 (2008).
2. Gruenewald, P. J. Regulating Availability: How Access to Alcohol Affects Drinking and Problems in Youth and Adults. *Alcohol Res. Health* **34**, 248–256 (2011).
3. Johnston, L. D. *et al.* *Demographic Subgroup Trends among Young Adults in the Use of Various Licit and Illicit Drugs, 1988-2016. Monitoring the Future Occasional Paper Series. Paper 89.* (Institute for Social Research, 2017).
4. Schulenberg, J. *et al.* *Monitoring the Future national survey results on drug use, 1975–2016: Volume II, College students and adults ages 19–55.* <http://monitoringthefuture.org/pubs.html#monographs> (2017).
5. Patrick, M. E. & Terry-McElrath, Y. M. High-Intensity Drinking by Underage Young Adults in the United States. *Addict. Abingdon Engl.* **112**, 82–93 (2017).
6. Patrick, M. E., Terry-McElrath, Y. M., Kloska, D. D. & Schulenberg, J. E. High-Intensity Drinking Among Young Adults in the United States: Prevalence, Frequency, and Developmental Change. *Alcohol. Clin. Exp. Res.* **40**, 1905–1912 (2016).
7. Nelson, T. F., Toomey, T. L., Lenk, K. M., Erickson, D. J. & Winters, K. C. Implementation of NIAAA College Drinking Task Force Recommendations: How Are Colleges Doing 6 Years Later? *Alcohol. Clin. Exp. Res.* **34**, 1687–1693 (2010).

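### Randomisation is blocked on morning/afternoon, but the models leave time of day out; if it predicts drinking, standard errors for the BA contrast on outcome levels will be too large.

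*Combined protocol and SAP*

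**What the plan says.** The Randomization section restricts allocation on two factors: "Randomization will employ blocking across morning and afternoon times and will occur within years". Under Participant Recruitment and Enrollment the plan adds: "The 36 sections will be paired such that BA and SO classes will be offered at the same time of day". Neither section gives a reason for blocking on time of day or an expected size for any difference between slots.

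The Data Analysis Plan lists the section-level terms as "Fixed effects for intervention condition (BA or SO), instructor, and" "cohort will be included at the class section level". At student level it adds one more: "Sex will also be added as a fixed effect at level 2". Year is therefore represented, through cohort. No term for morning/afternoon or for the pair is listed, and the omission is not explained. The plan then says of its models: "This approach will result in models with appropriate standard errors for the clustered sample". That sentence speaks to clustering and not to blocking.

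The Statistical Power section gives the size of the trial as "A target course section N of 36 (N=18 BA and N=18 SO), with N=432 participants total", for d=.43. It states no alpha, power or intraclass correlation (ICC).

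**The concern.** An analysis should normally carry the factors on which randomisation was restricted. Here one of two is carried. When BA and SO sections are balanced within slot, a morning/afternoon difference in outcome cancels from the BA minus SO contrast, so it adds nothing to the true sampling variance of the estimate. A model with no slot term still leaves that difference in the between-section variance from which the standard error is computed. The reported interval is then wider than the design warrants, and the test rejects less often than its nominal level.

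Power and interval width are at stake, not false-positive control. Students choose their sections through ordinary course registration, so slots could attract different students. The documents do not say whether they do.

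**Working it through.** **The plan's own figures.** 18 students x 0.85 consent = 15.3, taken as 15 per section. 36 x 15 = 540. 540 x 0.80 = 432. 432 / 36 = 12 analysed per section. This chain reproduces. The claim for d=.43 cannot be confirmed, because alpha, power and ICC are not given. At two-sided 0.05 and 80% power, 85 per arm are needed without clustering. 216/85 = 2.541 as a design effect, and (2.541 - 1)/11 gives an implied ICC of about 0.14. A t calculation on 34 df gives about 0.127 for 80% power.

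**Inputs for the illustration.** From the documents: 18 sections per arm, 12 per section, d=0.43. Assumed: two-sided alpha 0.05, unit total SD within slot, within-slot ICC 0.10 or 0.127, slot difference delta of 0.3 or 0.5 SD, equal numbers of morning and afternoon sections, BA and SO balanced within slot. The outcome is a section mean at one time point; instructor effects and repeated measures are left out.

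**Formulas.**
- True section-mean variance: V = ICC + (1 - ICC)/12.
- Variance used when slot is omitted: U = V + delta²/4.
- True SE = sqrt(2V/18); SE used = sqrt(2U/18).
- Power with slot in the model: Φ(0.43/SE_true - 1.96).
- Power with slot omitted: Φ((0.43 - 1.96 x SE_used)/SE_true). The inflated SE sets the critical value only; the estimate still varies with the true SE.
- Actual type I error with slot omitted: 2 x [1 - Φ(1.96 x SE_used/SE_true)].

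**Results.**

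| ICC | delta | V | U | U/V | SE true | SE used | Power, slot in | Power, slot out | Type I, slot out |
|---|---|---|---|---|---|---|---|---|---|
| 0.10 | 0.3 | 0.1750 | 0.1975 | 1.13 | 0.139 | 0.148 | 86.9% | 84.2% | 3.7% |
| 0.10 | 0.5 | 0.1750 | 0.2375 | 1.36 | 0.139 | 0.162 | 86.9% | 78.8% | 2.2% |
| 0.127 | 0.3 | 0.1998 | 0.2223 | 1.11 | 0.149 | 0.157 | 82.3% | 79.4% | 3.9% |
| 0.127 | 0.5 | 0.1998 | 0.2623 | 1.31 | 0.149 | 0.171 | 82.3% | 73.9% | 2.5% |

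The variance used is inflated by 11 to 36%, and the power loss is about 3 to 8 percentage points.

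**Check by simulation.** In 20,000 runs of 36 section means with cohort in the model, ICC was the total between-section share and f the part of it due to slot.
- f = 0 (ICC 0.02): model SE 0.106 against an empirical SD of 0.106; type I error 5.0%.
- ICC 0.02, f = 0.25: power 97.8% with slot omitted, 98.1% with it included.
- ICC 0.05, f = 0.25: model SE 0.121 against 0.114; power 94.0% and 95.3%.
- ICC 0.14, f = 0.50: model SE 0.157 against 0.127; type I error 1.5%; power 80.1% and 91.3%.

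In every scenario the empirical SD of the estimate was the same with and without the slot term.

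**The case against.** The strongest reply is that the harm is conditional, in the safe direction, and perhaps small. Most of that stands.

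- **No evidence of a slot effect.** A reader might infer that the standard errors are too large as a matter of fact, or that the plan blocked because morning and afternoon students drink differently. The documents support neither: no reason for blocking is stated and no slot difference is given. If slot is unrelated to outcome, the standard errors are correct.
- **The blocking is not wasted.** It is tempting to say that its precision is lost. It is not, because the balance still reduces the true variance of the estimate. What is missing is credit for it in the reported SE, interval and p-value. For the same reason, putting the inflated SE into both parts of the power formula, which gives 71-83% with slot omitted, overstates the loss.
- **The illustration leans large.** A slot difference of 0.5 SD exceeds the trial's target effect of 0.43. Added to a within-slot ICC of 0.10 to 0.127, the assumed differences imply overall ICCs of about 0.12 to 0.18. At ICC 0.02 to 0.05 with a modest slot share, the loss is about one point of power or less.
- **Slopes.** The plan's primary interest covers both intercepts and slopes. A constant slot difference largely cancels from within-student change, so slope tests suffer mainly if slot also alters change over time.
- **Instructor.** If instructors teach at fixed times, their fixed effects may absorb some slot variation. The documents do not say how instructors map to slots.
- **Binary outcome.** In the GLIMMIX model for the AUDIT cut-off, adding a covariate also changes the conditional odds ratio, so the linear argument does not carry over directly.

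These points limit the size and reach of the problem. None explains why one randomisation factor is modelled and the other is not.

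**Conclusion.** The mismatch between randomisation and analysis is plain from the text. Its consequence is conditional. If time of day predicts drinking and instructor effects do not already absorb it, the continuous models will overstate the standard error of the BA contrast on outcome levels, and the tests will be conservative. There is no bias and no type I inflation.

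Under the assumed ICC of 0.10 to 0.127 and slot difference of 0.3 to 0.5 SD, power at d=0.43 falls from about 82-87% to about 74-84%. The effect shrinks to nothing as the slot effect goes to zero, and it is trivial at small ICCs. Neither the ICC nor the slot effect is in the documents, so these figures show a plausible range and do not estimate what will happen in this trial. The point is worth correcting because the remedy is nearly free and the Statistical Power section treats 432 participants as what is needed, with no stated reserve. It is not a flaw that would invalidate the trial's conclusions.

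**What to change.** Prespecify morning/afternoon as a section-level fixed effect alongside cohort, or state why it is left out. Where slopes are tested, add a slot-by-time term, since a main effect alone would not adjust change over time. For the binary AUDIT outcome, say that the odds ratio is then conditional on slot.

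Do not fit 18 pair effects instead. With cohort in the model, one slot term moves the residual df from 31 to 30 and the critical t from 2.040 to 2.042. Pair effects would leave about 17 df (critical t 2.11) and can lose power when the slot effect is small: at ICC 0.10 with no slot effect, from 85.2% to 83.5%.

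The cost is about one section-level degree of freedom per term (with time entered linearly) and one sentence in the plan. No new data are needed, because the slot is known for every section. The choice should be fixed before outcomes are examined, so that it is not a discretionary one.

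### The ARSS-AUV score multiplies total frequency by total enjoyment, so within one alcohol context the reinforcement mediator ignores whether the activities done are the enjoyable ones

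*Combined protocol and SAP*

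**What the plan says.** Under Measures, Reinforcement Processes (Environmental reinforcement), the ARSS-AUV "assesses the frequency of past-month engagement in and enjoyment derived from 45 activities". The two contexts are asked separately: "Each question is posed twice - once to assess the frequency and enjoyment of the activity while using alcohol", and once for the activity without alcohol. The scoring rule is: "Frequency and enjoyment items are summed to form respective scores and then multiplied to form subscales for alcohol-related reinforcement and alcohol-free reinforcement". The final step is: "The two subscales are used to calculate the outcome, the total reinforcement ratio (TRR) between alcohol-related and alcohol-free reinforcement".

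The Data Analysis Plan gives the score its role: "Analyses will be conducted to determine whether changes in environmental reinforcement and delay discounting mediate the association between intervention condition and alcohol outcomes".

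Under Course and Intervention Content, the goal of BA for alcohol use is to "identify, develop and reinforce healthy behaviors that can serve as alternatives to alcohol use", and one of its four components is "identifying and engaging in reinforcing activities that align with their values". In Table 1, students rate the enjoyment of their activities from Week 1 and plan activities from Week 3.

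The plan does not give the response range of the items, the formula of the total reinforcement ratio (TRR), or the enjoyment score for an activity not done in the past month.

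**The concern.** The stated order is to sum the frequencies, sum the enjoyment ratings, and then multiply the two totals. The product depends on the totals alone. It does not record whether a student spends the time on activities that they enjoy or on activities that they do not, although the questionnaire collects both answers for each activity.

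BA asks students to rate activities and to engage in the reinforcing ones, so that pairing is part of the mechanism under test. If it is lost, a null mediation result could partly reflect the scoring, and a positive one could partly reflect a larger volume of activity of any kind.

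**Working it through.** **Inputs.** From the Measures section: 45 activities, frequency and enjoyment for each, two contexts, and the sum-then-multiply rule. Assumed for illustration only: ratings of 0-4, and the rating patterns below. The plan states no figure for this score, so there is none to reproduce.

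**Two scores compared, within one context.** With frequency f and enjoyment e for each activity:
- plan: S1 = (sum of f) x (sum of e)
- per activity: S2 = sum of (f x e)

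**1. Algebra (holds for any rating scale).** Hold the enjoyment ratings fixed and move d points of frequency from activity j to activity k. Both totals stay the same, so S1 changes by 0. S2 changes by d x (e_k - e_j). If d points are added to activity k and none are removed, S1 rises by d x (sum of e) whichever activity it is. S2 rises by d x e_k.

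**2. Base case for the 45-item illustrations.**
- Alcohol-free enjoyment is 0, 2 and 4 on 15 activities each: 15 x (0 + 2 + 4) = 90.
- Alcohol-free frequency is 3, 2 and 1 on the same groups: 15 x (3 + 2 + 1) = 90.
- S1 = 90 x 90 = 8,100. S2 = 15 x (3x0 + 2x2 + 1x4) = 120.
- With alcohol, enjoyment is 2 on all 45 activities (total 90) and frequency is 1 on 15 of them (total 15). S1 = 15 x 90 = 1,350. S2 = 15 x (1x2) = 30.
- The TRR is taken here as alcohol-related / (alcohol-related + alcohol-free), because the plan does not give the formula. S1: 1,350/9,450 = 0.143. S2: 30/150 = 0.200.

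**3. Shift toward enjoyable activities within the alcohol-free context.** Frequency becomes 1, 2 and 3. The total is still 90, and every alcohol-free activity is done both before and after.
- S1 = 8,100 and TRR = 0.143, both unchanged.
- S2 = 15 x (1x0 + 2x2 + 3x4) = 240, and TRR = 30/270 = 0.111.

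**4. Ten points of alcohol-free activity added, none removed.**
- S1 = 100 x 90 = 9,000, whether the additions are at enjoyment 4 or at enjoyment 0.
- S2 = 120 + 10x4 = 160 for the enjoyable additions, and 120 + 10x0 = 120 for the unenjoyable ones.

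**5. Ten points moved from with-alcohol to enjoyable alcohol-free activity.**
- S1: alcohol-free 8,100 to 9,000; alcohol-related 1,350 to 5 x 90 = 450. TRR goes from 0.143 to 450/9,450 = 0.048. The plan's rule registers this.
- S2: 120 to 160 and 30 to 10. TRR goes from 0.200 to 10/170 = 0.059.

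**6. The shift in step 3, with enjoyment also up one point on 15 activities.** S1 = 90 x 105 = 9,450, so a change in the totals registers.

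**7. Random check.** In 20,000 random 45-item profiles, up to eight frequency points were moved from low- to high-enjoyment activities. The largest change in S1 was 0. S2 rose by 13.7% on average.

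**The case against.** **BA's stated alcohol goal is substitution.** It is to provide alternatives to drinking. The two contexts are scored separately, and the TRR moves when activity passes from one to the other (step 5). Planning and support would also plausibly raise total activity or enjoyment, and both register. This stands. A reader might infer that the mediator cannot detect the change BA is meant to cause. The documents do not support that: the blind spot needs one context, constant total frequency and constant enjoyment ratings.

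**The rule for activities not done is open.** Extreme examples depend on it. On a 0-4 scale, take one student at (frequency 4, enjoyment 4) on 22 activities, (2, 2) on one and (0, 0) on 22. Take another at (4, 0) on 22, (2, 2) on one and (0, 4) on 22. Both score 90 x 90 = 8,100 under the plan, against per-activity sums of 356 and 4. But the second student rates 22 activities never done as highly enjoyable. If activities not done score 0 for enjoyment, that student's plan score is 90 x 2 = 180, and the rule separates the two 45-fold. This also stands, but it is only a partial rescue. For two activities that are both done, with enjoyment 1 and 4, moving frequency from (4, 1) to (1, 4) leaves the plan's score at 5 x 5 = 25. The per-activity sum goes from 4x1 + 1x4 = 8 to 1x1 + 4x4 = 17.

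**The instrument may prescribe this scoring.** The plan cites a psychometric paper for the ARSS-AUV, and the documents do not reproduce its scoring. If that paper sums first, the plan follows its instrument, and replacing the score outright would cost comparability. If it takes per-activity products, the plan's sentence misdescribes the score and needs correcting. The documents cannot settle which. This is a reason to report both scores.

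**Conclusion.** The point holds in a limited form. As written, each subscale discards the pairing of engagement with enjoyment. Within one context it is blind to a shift toward more enjoyable activities at unchanged totals, and it credits added unenjoyable activity as fully as added enjoyable activity. The first result is exact and needs no assumption about the rating scale, only that total frequency and the enjoyment ratings stay fixed. The figures of 8,100, 120 to 240 and 13.7% are illustrations on assumed 0-4 ratings and assumed patterns. They do not estimate the effect in this trial, and the size of any bias in the mediated effect has not been computed.

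The loss concerns one change that BA aims for and one of two named mediators. It would be wrong to conclude that the mediation analysis is invalid, because the score still captures substitution across contexts and changes in the totals. The aim 1 outcomes (AUDIT cut-off, consumption and problems, and high-intensity drinking) do not use this score.

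**What to change.** In the Environmental reinforcement paragraph, prespecify a per-activity score: multiply frequency by enjoyment for each of the 45 activities, then sum the products, separately for the with-alcohol and without-alcohol versions. Form the TRR from these sums and use it in the mediation analysis. Report the sum-then-multiply TRR alongside, for comparability with whatever scoring the instrument's source prescribes.

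In the same paragraph, state the TRR formula and how enjoyment is scored for an activity not done in the past month. If per-activity products were intended all along, the sentence should say so.

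The cost is a few sentences in the plan, a line of scoring code and one extra analysis. Frequency and enjoyment are already asked for each activity, so participants do nothing more. The downside is a possible departure from the instrument's published scoring, which reporting both versions covers.
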